A central pathologist will confirm histopathological BPDCN diagnosis. Tumor response will be assessed by the Investigators for all patients with BPDCN, with the Investigator's assessment to be used in the primary analysis. As a supportive assessment, tumor response was also evaluated by an IRC on a pre-specified subset of patients.

2 Abbreviations and Definitions

AE	Adverse Event
ALL	Acute Lymphoid Leukemia
ALP	Alkaline Phosphatase
ALT	Alanine Transaminase
AML	Acute Myeloid Leukemia
ANC	Absolute Neutrophil Count
APL	Acute Promyelocytic Leukemia
Ara-C	Cytosine Arabinoside
AST	Aspartate Transaminase
BM	Bone Marrow
BMA	Bone Marrow Aspiration
BMCR	Bone Marrow Complete Response
BP	Blood Pressure
BPDCN	Blastic Plasmacytoid Dendritic Cell Neoplasm
BSA	Body Surface Area
BTD	Breakthrough Therapy Designation
BUN	Blood Urea Nitrogen
CBC	Complete Blood Count
CLS	Capillary Leak Syndrome
CML	Chronic Myeloid Leukemia
CNS	Central Nervous System
CPK	Creatine Phosphokinase
CR	Complete Response
CRc	CR [Clinical] with Minimal Residual Skin Abnormality
CRi	Complete Response with Incomplete Bone Marrow Recovery
CSC	Cancer Stem Cell
CT	Computed Tomography
CTCAE	Common Terminology Criteria for Adverse Events

DLT	Dose-Limiting Toxicity
DSRC	Data Safety Review Committee
DT	Diphtheria Toxin
ECG	Electrocardiogram
ECHO	Echocardiogram
ECOG	Eastern Cooperative Oncology Group
eCRF	Electronic Case Report Form
EDTA	Ethylenediamine Tetraacetic Acid
FDA	Food and Drug Administration
GLP	Good Laboratory Practice
GVHD	Graft Versus Host Disease
HIPAA	Human Insurance Portability Accountability Act
IB	Investigator Brochure
ICF	Informed Consent Form
ICH	International Council for Harmonisation
ICU	Intensive Care Unit
IHC	Immunohistochemistry
IND	Investigational New Drug Application
IRC	Independent Review Committee
IL-3	Interleukin-3
IL-3R	Interleukin-3 Receptor
INR	International Normalized Ratio
IV	Intravenous Administration
LDH	Lactate Dehydrogenase
LFT	Liver function test
LVEF	Left Ventricular Ejection Fraction
MDS	Myelodysplastic Syndrome
mITT	Modified intent-to-treat
mSWAT	Modified Severity Weighted Assessment Tool

MTD	Maximum Tolerated Dose
MUGA	Multigated Acquisition Scan
NCI	National Cancer Institute
ORR	Objective Response Rate
OS	Overall Survival
PD	Progressive Disease
pDCs	Plasmacytoid Dendritic Cells
PK	Pharmacokinetics
PFS	Progression-free Survival
PO	Orally
PP	Per-protocol
PR	Partial Response
PS	Performance Status
PT	Prothrombin Time
PTT	Partial Thromboplastin Time
RBC	Red Blood Cell
R/R	Relapsed/Refractory
rIL2	Recombinant Interleukin-2
SAE	Serious Adverse Event
SCT	Stem Cell Transplant
SD	Stable Disease
SGOT	Serum Glutamic Oxaloacetic Transaminase
SGPT	Serum Glutamic Pyruvic Transaminase
TEAE	Treatment-emergent adverse event
TLS	Tumor Lysis Syndrome
ULN	Upper Limit of Normal
VOD	Veno-occlusive disease
WHO	World Health Organization
WOCBP	Women of Childbearing Potential

3 Introduction and Study Rationale

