Patients who benefit from treatment and do not have evidence of clinically significant progressive disease may receive repeated cycles of SL-401 even if a response, in the judgment of the Investigator, is not attained. Patients should continue to receive SL-401 as long as they may be benefiting from treatment, according to the Investigator; no maximum duration of therapy has been set.

Patients will receive the following premedications approximately 60 minutes before each SL-401 infusion:

- Acetaminophen 650 mg (or equivalent dose of paracetamol) orally (PO)
- Diphenhydramine 50 mg IV (or equivalent dose of another H1-histamine antagonist)
- Methylprednisolone 50 mg IV (or an equivalent dose of another corticosteroid)
- Ranitidine 50 mg IV (or an equivalent dosage of another H₂-histamine antagonist)

During the dosing period for each cycle, individual SL-401 infusions may be delayed to allow for toxicity resolution, as detailed in [Section 7.5.5](#).

During the first cycle, patients will receive a starting dose according to their dosing cohort in Stage 1, or the dose carried into Stages 2-4. Potential dose modifications for subsequent cycles relative to the prior cycle dose will be based on the severity and resolution of toxicities. Dose reductions should be discussed with the medical monitor on a case by case basis.

Procedures During Dosing Period:

During each cycle, testing and procedures that may result in withholding of a scheduled SL-401 infusion, largely based on unresolved manifestations of fluid retention and/or other relevant acute toxicities during daily dosing, are described in [Table 5](#), [Table 6](#), [Table 7](#), and [Table 8](#) in Section 9.8.

Withhold SL-401 infusion if any of the following occur:

- Body temperature $\geq 38^{\circ}\text{C}$
- Heart rate ≥ 130 or ≤ 40 bpm
- Systolic blood pressure (BP) ≥ 160 or ≤ 80 mmHg
- Serum creatinine > 1.8 mg/dL (159 $\mu\text{mol/L}$)
- Serum albumin
 - In settings in which albumin is reduced to 3.0-3.5 g/dL (30-35 g/L) or by ≥ 0.5 g/dL (5 g/L) below the level at the start of the cycle, withhold SL-401 infusion and administer albumin 25 g IV daily or every 12 hours as clinically feasible until serum

albumin is both ≥ 3.5 g/dL and not reduced by ≥ 0.5 g/dL from the level at the start of the cycle prior to resuming treatment with SL-401 in the same cycle.

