- In settings in which albumin is reduced to <3.0 g/dL (30 g/L) or by more than 1.0 g/dL (10 g/L) below the level at the start of the cycle (i.e., from 4.3 g/dL to 3.2 g/dL), withhold SL-401 infusions for the duration of that particular cycle. Albumin should be administered until the albumin level is at least above 3.5g/dL. Consultation with the Medical Monitor is advised.
- Dosing in the next cycle may resume if albumin remains at 3.5 g/dL without additional albumin infusions.
- AST >5 times the ULN or ALT >5 times the ULN (SL-401 will be withheld for remainder of study cycle)
- Increase in body weight by ≥ 1.5 kg over pre-treatment weight on the prior treatment day.

Refer to [Section 7.5.5](#) for dose modifications/delays. Management procedures for capillary leak syndrome (CLS) and associated symptoms are provided in [Section 16.5, Appendix E](#).

Concomitant Medications:

Recommended Medications Per Institutional Guidelines/Practices:

It is recommended that patients receive the following types of prophylactic therapies/regimens per institutional guidelines/practices:

- Antibacterial: ciprofloxacin, levofloxacin, or an equivalent antibiotic
- Antifungal: fluconazole, voriconazole, or an equivalent antifungal
- Antiviral: acyclovir, valacyclovir or an equivalent antiviral

Allowed Medications/Therapies:

All patients may receive supportive care measures as clinically indicated, including prophylactic antibiotics, antihistamines, antiemetics, albumin, fluids (hydration), and supportive measures. Patients may receive growth factor support and/or blood product transfusions as per the discretion of their physician.

Albumin 25 g IV daily should be administered if serum albumin is between 3.0-3.5 g/dL (30-35 g/L) on days that dosing occurs or if it is <3.0 g/dL (30 g/L) on days when treatment has been withheld or in the immediate post-treatment period. The Investigator has discretion with regard to frequency of administration.

Prohibited Medications/Therapies:

An enrolled patient may not receive investigational or approved anticancer or anti-leukemia agents, including cytotoxic chemotherapy agents, hypomethylating agents (5-azacytidine, decitabine or others), or anticancer tyrosine kinase inhibitors (including imatinib, ruxolitinib, sorafenib and others) or therapeutic monoclonal antibodies. Hydroxyurea may be administered (however its use should be discussed with the Medical Monitor).

Assessments:

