The LFT and albumin findings from SL-401 in Study 50047 indicate that most patients with clinically meaningful changes in these parameters following administration of SL-401 would be expected to recover to near baseline levels by 3-4 weeks following the initiation of therapy. These results therefore support administration of cycles every 3 weeks with the allowance to delay the start of a subsequent cycle to allow toxicity resolution. This has been confirmed during Stage 1 of the current study, where the majority of patients have been able to receive multiple cycles of SL-401 despite transaminase elevations and hypoalbuminemia during Cycle 1. CLS was the principal DLT in Study 50047 and in the current study. Similarly, CLS is an event associated with treatment with approved doses of denileukin ditox (Ontak®), a Food and Drug

Administration (FDA)-approved treatment for patients with persistent or recurrent cutaneous T-cell lymphoma whose malignant cells express the IL-2 receptor. Treatment of patients with SL-401 at doses below those in which multiple cases of severe CLS were observed in Study 50047 is one element by which the risk of this SL-401-associated toxicity will be minimized in the current study.

During Study 50047, risk mitigation measures for CLS were implemented. These included premedication (e.g., an H₁-histamine antagonist, acetaminophen, and a corticosteroid); administration of IV albumin if serum albumin decreased to <3 g/dL; and a diuretic regimen (e.g., furosemide) if patients experienced >10% weight gain (with no hypotension) concurrent with the administration of a basal parenteral hydration to maintain intravascular volume. In the peri-treatment period, vital signs, weight, serum electrolytes, and albumin were monitored. Similar measures have been incorporated into the current study, as described in [Section 7.5.4](#). Additional precautions, including a requirement that patients have a normal cardiac ejection fraction at study entry, and requiring withholding of treatment in the setting of albumin reductions or weight increases during the dosing period, similar to recommendations concerning the optimal administration of denileukin diftitox, have also been implemented ([McCann et al. 2012](#), [Olsen et al. 2001](#), [Prince et al. 2009](#)).

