7.5.5 Dose Delays/Modifications and Management Procedures for Toxicities Associated with SL-401

During the dosing period for each cycle, individual SL-401 infusions may be delayed to allow for toxicity resolution. Details are presented in [Table 4](#).

Monitor vital signs and check albumin, transaminases, and creatinine prior to preparing each dose of ELZONRIS.

Table 4: Recommended ELZONRIS Dose Modifications

Parameter	Severity Criteria	Dose Modification
Serum albumin	Serum albumin < 3.5 g/dL or reduced \geq 0.5 g/dL from value measured prior to initiation of the current cycle	See CLS Management Guidelines (Appendix E)
Body weight	Body weight increase \geq 1.5 kg over pretreatment weight on prior treatment day	See CLS Management Guidelines (Appendix E)
Aspartate aminotransferase (AST) or alanine aminotransferase (ALT)	ALT or AST increase $>$ 5 times the upper limit of normal	Withhold SL-401 until transaminase elevations are \leq 2.5 times the upper limit of normal.
Serum creatinine	Serum creatinine $>$ 1.8 mg/dL (159 micromol/L) or creatinine clearance $<$ 60 mL/minute	Withhold SL-401 until serum creatinine resolves to \leq 1.8 mg/dL (159 micromol/L) or creatinine clearance \geq 60 mL/minute.
Systolic blood pressure	Systolic blood pressure \geq 160 mmHg or \leq 80 mmHg	Withhold SL-401 until systolic blood pressure is $<$ 160 mmHg or $>$ 80 mmHg.
Heart rate	Heart rate \geq 130 bpm or \leq 40 bpm	Withhold SL-401 until heart rate is $<$ 130 bpm or $>$ 40 bpm.
Body temperature	Body temperature \geq 38°C	Withhold SL-401 until body temperature is $<$ 38°C.
Hypersensitivity reactions	Mild or moderate	Withhold SL-401 until resolution of any mild or moderate hypersensitivity reaction. Resume ELZONRIS at the same infusion rate.
	Severe or life-threatening	Discontinue SL-401 permanently.

Dose reductions should be discussed with the medical monitor on a case by case basis.

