16.5 Appendix E. CLS Management Guidance

Time of Presentation	CLS Sign/Symptom	Recommended Action	ELZONRIS Dosing Management
Prior to first dose of ELZONRIS in cycle 1	Serum albumin < 3.2 g/dL	Administer ELZONRIS when serum albumin \geq 3.2 g/dL.	
During ELZONRIS dosing	Serum albumin < 3.5 g/dL		Interrupt ELZONRIS dosing until the relevant CLS sign/symptom has resolved ¹ .
	Serum albumin reduced by \geq 0.5 g/dL from the albumin value measured prior to ELZONRIS dosing initiation of the current cycle	Administer 25g intravenous albumin (q12h or more frequently as practical) until serum albumin is \geq 3.5 g/dL AND not more than 0.5 g/dL lower than the value measured prior to dosing initiation of the current cycle.	
	A predose body weight that is increased by \geq 1.5 kg over the previous day's predose weight	Administer 25g intravenous albumin (q12h or more frequently as practical), and manage fluid status as indicated clinically (e.g., generally with intravenous fluids and vasopressors if hypotensive and with diuretics if normotensive or hypertensive), until body weight increase has resolved (i.e. the increase is no longer \geq 1.5 kg greater than the previous day's predose weight).	
	Edema, fluid overload and/or hypotension	Administer 25g intravenous albumin (q12h, or more frequently as practical) until serum albumin is \geq 3.5 g/dL. Administer 1 mg/kg of methylprednisolone (or an equivalent) per day, until resolution of CLS sign/symptom or as indicated clinically. Aggressive management of fluid status and hypotension if present, which could include intravenous fluids and/or diuretics or other blood pressure management, until resolution of CLS sign/symptom or as clinically indicated.	

¹ ELZONRIS administration may resume in the same cycle if all CLS signs/symptoms have resolved and the patient did not require measures to treat hemodynamic instability. ELZONRIS administration should be held for the remainder of the cycle if CLS signs/symptoms have not resolved or the patient required measures to treat hemodynamic instability (e.g. required administration of intravenous fluids and/or vasopressors to treat hypotension) (even if resolved), and ELZONRIS administration may only resume in the next cycle if all CLS signs/symptoms have resolved, and the patient is hemodynamically stable.

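### For a severe albumin fall, the Synopsis stops SL-401 for the cycle, while Table 4 and Appendix E permit dosing to resume in the same cycle

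*Protocol*

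**What the plan says.** **Synopsis, Procedures During Dosing Period.** There are two albumin tiers. In the milder one (3.0 to 3.5 g/dL, or a fall of at least 0.5 g/dL), SL-401 is held and albumin given until the value recovers, measured "from the level at the start of the cycle prior to resuming treatment with SL-401 in the same cycle". In the severe one (below 3.0 g/dL, or a fall of more than 1.0 g/dL), the rule, with its worked example, reads "i.e., from 4.3 g/dL to 3.2 g/dL), withhold SL-401 infusions for the duration of that particular cycle". Medical Monitor consultation is advised, and for later dosing the text adds: "Dosing in the next cycle may resume if albumin remains at 3.5 g/dL without additional albumin infusions".

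**Section 7.5.5, Table 4.** There is one albumin tier (below 3.5 g/dL, or a fall of at least 0.5 g/dL), which refers the reader to Appendix E. Section 8.9 also sends albumin changes there.

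**Section 16.5, Appendix E.** There is no severe tier. The recovery target after a fall is at least 3.5 g/dL and "not more than 0.5 g/dL lower than the value measured prior to dosing initiation of the current cycle". Footnote 1 then says "ELZONRIS administration may resume in the same cycle if all CLS signs/symptoms have resolved", provided the patient did not need measures for hemodynamic instability. If signs persist or such measures were needed, dosing is held for the rest of the cycle.

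**AST or ALT above 5 times ULN.** The Synopsis says "SL-401 will be withheld for remainder of study cycle". Table 4 says "Withhold SL-401 until transaminase elevations are" at or below 2.5 times ULN, and does not mention the cycle.

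**Other Table 4 release cells.** Systolic pressure (<160 *or* >80 mmHg), heart rate (<130 *or* >40 bpm) and renal function (creatinine ≤1.8 mg/dL *or* clearance ≥60 mL/min) each join two limits with *or*.

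**The concern.** Section 3.8 states that "CLS was the principal DLT in Study 50047 and in the current study", and the albumin hold is one of the protocol's main protections against it. For the same laboratory value, one part of the protocol ends the cycle and another lets the patient be dosed again within days. The Synopsis points to Section 7.5.5 and Appendix E, but it keeps its own stop and does not say which text governs.

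There is a reporting consequence as well. Redosing in the same cycle after albumin below 3.0 g/dL departs from the Synopsis yet can comply with Appendix E. The protocol-violation review in SAP 2.2 therefore has no single standard for it.

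**Working it through.** The plan gives no figure to reproduce; the check compares the rules.

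**1. Does every Synopsis stop fall under the Appendix E permission?** Yes, by logic. Albumin below 3.0 is also below 3.5, and a fall above 1.0 is also a fall of at least 0.5. So every patient in the severe tier meets the Table 4 trigger and is handled by Appendix E. A grid confirms it: with starting albumin 3.2 to 5.0 g/dL and on-treatment albumin from 2.0 up to the start, in steps of 0.1, all 245 points that the Synopsis stops are ones Appendix E interrupts with possible same-cycle resumption. The protocol's own example, a fall of 4.3 − 3.2 = 1.1 g/dL, is among them.

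**2. Where the thresholds lie.** The Synopsis stop applies below max(3.0, start − 1.0). The Appendix E recovery target is max(3.5, start − 0.5).

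| Start of cycle (g/dL) | Synopsis stops below | Appendix E target |
|---|---|---|
| 4.0 | 3.0 | 3.5 |
| 4.3 | 3.3 | 3.8 |
| 4.5 | 3.5 | 4.0 |

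**3. Largest possible dose difference in one affected cycle.** Inputs: 12 µg/kg/day (Section 7.5.2), 5 infusions, so 5 × 12 = 60 µg/kg planned; infusions to be completed within 10 days (Section 9.8, Table 7 footnote n). If the fall is found before infusion k, the Synopsis total is 12(k − 1), the Appendix E maximum is 60, and the gap is 60 − 12(k − 1).

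| Found before infusion | Synopsis total (µg/kg) | Maximum gap (µg/kg) | Share of 60 | Latest day to resume and finish by Day 10 |
|---|---|---|---|---|
| 2 | 12 | 48 | 80% | 7 |
| 3 | 24 | 36 | 60% | 8 |
| 4 | 36 | 24 | 40% | 9 |
| 5 | 48 | 12 | 20% | 10 |

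The last column assumes daily infusions. The gap reaches its maximum only if every sign resolves by that day.

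**4. Timing.** In the earlier single-cycle study, albumin was lowest about one week after the first infusion and liver tests peaked at about two weeks (Section 3.7.1). The albumin question can therefore arise inside the 10-day window. A transaminase recovery to 2.5 times ULN inside it is less likely.

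**5. The *or* cells.** Every systolic value is below 160 or above 80, and every heart rate is below 130 or above 40, so both release conditions are always true. Over 40 to 260 mmHg all 142 hold-triggering values also meet release; over 20 to 220 bpm all 112 do. With *and*, none do. For the renal cell, take creatinine 1.2 mg/dL with clearance 50 mL/min, or creatinine 2.0 with clearance 70. Each meets the hold and, under *or*, also meets release; under *and*, neither is released.

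**The case against.** **A permission and a restriction can coexist.** Appendix E is guidance, says dosing may resume, and attaches conditions. A site that stops for the cycle breaches neither text. That stands, and it makes the Synopsis stop a safe interim rule. It does not reconcile the texts: a site that resumes as Appendix E allows breaches the Synopsis.

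**The body text may be the newer one.** Section 3.8 says Amendment 12 modified procedures to follow the approved package insert, which suggests that Table 4 and Appendix E were updated and the Synopsis was not. That is inference; nothing withdraws the Synopsis stop.

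**It comes late.** The current text cites the approval of 21 December 2018. SAP 1.1 puts the end of Stage 4 enrollment at January 7, 2019, 17 days later, and SAP 3.13.4 gives a data cutoff of 13 March 2020, 448 days after approval. The text therefore mainly concerns patients already on treatment, and no document shows how many were still being dosed. This stands and limits the size of the point.

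**Stronger readings a reader might infer, which the documents do not support:**

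- *The AST/ALT rules contradict each other.* They can be read together: stop for the cycle, then restart at or below 2.5 times ULN. Table 4 never states that dosing may resume in the same cycle.
- *The renal cell plainly needs* and. Clearance is absent from the entry criteria (Section 5.2 requires only creatinine ≤1.5 mg/dL), from the Synopsis trigger and from the laboratory lists in Sections 7.5.4 and 8.9. Under *and*, an eligible patient with clearance below 60 would stay held.
- *The blood pressure and heart-rate holds never bind.* That is true of the literal wording only. The intent is clear, and vital signs are checked before each dose.

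**Conclusion.** The albumin conflict is real, explicit and in current text. It should be fixed because it concerns a stopping rule for the principal dose-limiting toxicity. The 20% to 80% figures are ceilings for a single affected cycle, not an estimated effect. They carry no event frequency, and the largest ones need an early severe fall, which the one-week nadir in the earlier study does not favor. The documents do not count holds, so the number of patients affected cannot be given; it is probably small. Nothing shows that sites followed different rules or that a patient was harmed. There is no effect on alpha, power or the primary endpoint.

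The systolic pressure and heart-rate cells are wording errors with little practical effect. The renal cell is ambiguous, and the AST/ALT texts need clarifying rather than reconciling.

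**What to change.** 1. **Albumin.** State one rule for albumin below 3.0 g/dL or a fall above 1.0 g/dL in the Synopsis, Table 4 and Appendix E. The sponsor's clinicians choose it. Until then apply the Synopsis stop, which complies with both texts.
2. **Systolic pressure and heart rate.** Change *or* to *and* in the two release cells.
3. **Renal cell.** First decide whether the clearance trigger applies and how clearance is obtained. Then let release require that no applicable trigger is still met. Do not change the word on its own.
4. **AST/ALT.** Add to Table 4 that dosing stops for the cycle and restarts in a later cycle only at or below 2.5 times ULN.

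The cost is one protocol clarification or amendment, with no new data collection for items 1, 2 and 4; item 3 may need a clearance calculation if that trigger is kept. The interim albumin stop costs an affected patient up to 1 to 4 infusions of that cycle, depending on when the fall is found. The by-patient exposure and laboratory listings already planned in SAP 4.4.1 and 4.4.3 would let the sponsor count infusions given in the same cycle after a severe albumin fall.

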3.1 Blastic Plasmacytoid Dendritic Cell Neoplasm

Blastic plasmacytoid dendritic cell neoplasm (BPDCN) is an uncommon hematological malignancy characterized by the clonal proliferation of malignant plasmacytoid dendritic cells (pDCs) (Facchetti et al. 2003). This neoplasm was originally recognized as a distinct entity in 1994 (Adachi et al. 1994) and the uncertainty regarding its histogenesis was reflected by the multiplicity of terms that were previously used for its designation, including agranular CD4+ natural killer cell leukemia (Brody et al. 1995), blastic natural killer leukemia/lymphoma (DiGiuseppe et al. 1997), and agranular CD4+/CD56+ hematodermic neoplasm (Petrella et al 2002; Herling et al. 2007). In 2001, the World Health Organization (WHO) classification of tumors of hematopoietic and lymphoid tissue proposed the term blastic natural killer (NK) cell lymphoma on the basis of the blastic cytology, and the expression of CD56 in the absence of other lineage specific markers. The relationship of BPDCN to pDCs was hypothesized first by Lucio et al. (1999) and subsequently confirmed by several studies (Petrella et al. 2002; Jacob et al. 2003; Reichard et al. 2005; Urosevic et al. 2005; Chaperot et al. 2004; Bene et al. 2003). The term BPDCN was introduced in 2008 by the updated WHO classification (4th edition) (Facchetti et al. 2008).

BPDCN most commonly affects middle-aged and older patients and is approximately 3.5-fold more common in men than women. The median age at diagnosis is 66 years and is lower for women than men. The true incidence and prevalence of BPDCN, like many other rare diseases without definitive and/or effective therapy, is not precisely known. However, based on a published report (Wang et al. 2012), BPDCN may constitute approximately 0.44% of the incident cases of hematologic cancers annually, or approximately 700 and 1,000 incident cases annually in the United States (US) and Europe, respectively, based on published data of hematologic cancer cases.

BPDCN cells show an immature “blastic” appearance; the diagnosis rests upon the demonstration of CD4 and CD56 expression, together with markers more restricted to PDC (such as CD123 [or the interleukin-3 receptor; IL-3R]) and negativity for lymphoid, NK and myeloid lineage-associated antigens. Immunophenotypic markers frequently, variably and infrequently expressed in BPDCN are detailed in Table 1 (Chaperot et al. 2001, Facchetti et al. 2008, Garnache-Ottou et al. 2009, Herling et al. 2007, Marafioti et al. 2008, Shi et al 2014, Zheng et al. 2012). The diagnosis of BPDCN is enabled by comprehensive evaluation of overall clinical manifestations, the morphologic appearance of blasts on skin, marrow or other biopsy, and a characteristic immunophenotypic profile, as indicated in Table 1.

Table 1: Immunophenotypic Marker Expression in BPDCN

Immunophenotypic Marker	Description
Frequently expressed in BPDCN	
CD4, CD56, CD123 (IL-R3 α)	Widely recognized BPDCN markers with significant expression in substantial majority of BPDCN cases.
TCL1(TCL1A) (T cell leukemia/lymphoma)	Lymphoid marker, expressed in majority of BPDCN (and also normal pDCs); also expressed in B- and T-cell ALL.
BDCA-2/CD303	Dendritic cell marker frequently expressed in BPDCN and infrequently expressed in other acute leukemias.
BDCA-4/Neuropilin-1	Dendritic cell marker frequently expressed in BPDCN; may also be expressed in other acute leukemias.
CD2AP (CD2-associated protein)	Adaptor protein frequently expressed in pDCs and BPDCN and infrequently expressed in other acute leukemias.
CD45-RA	T-lymphoid marker, frequently expressed in BPDCN; may also be expressed in acute lymphoid malignancies.
Variably expressed in BPDCN	
HLA-DR	Myeloid precursor with variable expression in BPDCN; may also be expressed in acute myeloid leukemias.
Infrequently expressed in BPDCN	
CD11c, MPO (myeloperoxidase)	Myeloid markers, negative in majority of BPDCN cases.
CD79a	B-lymphoid marker, negative in majority of BPDCN cases.
CD3	T-lymphoid marker, negative in majority of BPDCN cases.

The clinical features and evolution of BPDCN are homogeneous, primarily consisting of 2 patterns (Brody et al. 1995; Herling et al. 2007; Reichard et al. 2005; Petrella et al. 2005; Petrella et al. 1999; Suzuki et al. 2005; Assaf et al. 2007). The first pattern (90% of cases) is characterized by an indolent onset dominated by cutaneous lesions followed by tumor dissemination. The second pattern shows features of an acute leukemia with systemic involvement from the outset, and multiple skin nodules are frequently present (Suzuki et al. 2005). BPDCN most typically presents with skin lesions, as well as extracutaneous malignant disease in the bone marrow, blood, lymph nodes, spleen, and other organs. Despite the frequent appearance of a somewhat indolent clinical presentation at the outset, the course of BPDCN is highly aggressive and the median survival is approximately 12-14 months (Herling et al. 2007; Jacob et al. 2003; Petrella et al. 2005; Bekkenk et al. 2004; Feuillard et al. 2002). The disease also almost always results in a terminal leukemic phase with proliferation of BPDCN blasts in the bone marrow and peripheral blood, leading to decreased blood cell counts with resultant infections, bleeding, and invariably death.

There is currently no standard of care, nor an effective treatment regimen, for BPDCN (Riaz et al. 2014). Previously untreated (first-line) BPDCN patients are typically treated with combination chemotherapy regimens generally used for lymphoma or acute leukemia, often requiring dose reductions or elimination of anthracyclines due to the predominance of elderly patients with this disease. There are only a few large studies (over 40 patients) reported in the literature; the most recent and largest, with over 80 patients, reported a 56% response rate in first-line BPDCN with combination chemotherapy, but response criteria were not elucidated. Median overall survival (OS) from diagnosis is only 8 to 14 months, with elderly patients being at the lower end of this range. Allogeneic stem cell transplant, mostly reserved for younger patients in first complete response (CR) with good performance status, has also been employed but only when patients' disease state and overall physical condition permit. Furthermore, the literature for the treatment of relapsed/refractory (R/R) BPDCN is scattered, limited and inconsistent in the way that clinical benefit is measured and presented, and management beyond first-line is usually not described in the larger retrospective case studies; of 7 published studies involving ≥ 10 patients, there is only one documented response to ≥ 2 lines of therapy.

